Study Protocol and Statistical Analysis Plan

Title: Occupational Performance Coaching With Parents of Young Children With Developmental Disability

NCT number: NCT04796909

Document date: 22 July 2020

1 Introduction

High rates of restricted community participation have been reported in young children with developmental disabilities. Occupational performance coaching (OPC), grounded in self-determination theory, aims to facilitate children's participation in life situations through coaching parents. However, there have been limited randomized controlled trials demonstrating the efficacy of OPC, especially with a specific focus on children's community participation. The proposed study is the first step in evaluating the feasibility and acceptability of conducting a pilot randomized controlled trial of OPC in Hong Kong and testing its initial efficacy (in comparison to parent consultation) in promoting children's community participation.

In this document, we report a study protocol that will be used in the Phase 1 Randomized Control Trial (RCT) which aims to evaluate the feasibility of conducting an RCT of OPC in Hong Kong, the acceptability of the coaching intervention, and the initial efficacy of OPC on promoting children's community participation.

2 Materials and Methods

2.1 Trial Design

We propose a two-arm parallel, double-blind design for this Phase 1 RCT of OPC. Parents of young children with DD will be randomly assigned to the intervention group (receiving OPC), and the control group (receiving parent consultation) and will be blinded to the group type that they are assigned to. Parent consultation is chosen as the component-equivalent control treatment, because it is a common approach used by rehabilitation therapists to improve children's adaptive behavior and parenting skills. Meanwhile, both groups will continue to receive usual care during the study period. The trial design is illustrated in Figure 1. The present protocol was prepared according to the recommendation for good practice in RCT feasibility and pilot design.

2.2 Study Setting and Participants

The RCT will be conducted in Hong Kong across three major geographical regions (Hong Kong Island, Kowloon, and New Territories). The target population will comprise families with young children awaiting or receiving early intervention services. To be eligible for the study, participants will have to (a) be one/both parent(s) of a child aged 2–6 years old who have been clinically diagnosed with a DD (including but not limited to intellectual disability, developmental delay, or autism spectrum disorder) given by pediatricians/psychiatrists; (b) be the child's main caregiver who has a long-term parenting

role with at least 50% of caregiving responsibilities; (c) be able to converse in Chinese; and (d) have the desire to improve their child's participation in four community activities that are selected from the Young Children's Participation and Environment Measure (YC-PEM, detailed later).

Participants will be excluded if their child has DD combined with physical impairment (e.g., amputation, cerebral palsy, spina bifida) or sensory impairment (e.g., blindness, deafness). This is because the support and resources needed to improve community participation for these children may differ from those for children with DD without physical/sensory constraints.

2.3 Sample Size

The sample size was calculated using Morgan and Case's formula with the following set-up: type I error of 0.05, power of 0.90, 1-to-1 random allocation, and variance ratio of 0.44, using a conservative assumption for the compound symmetry correlation structure. A large effect size (Cohen's d) of 0.80 was determined based on the pooled effect sizes derived from our previous study and a recent RCT. Therefore, a minimum sample size of 30 participants will be required in this pilot RCT to test for 2×3 mixed design analysis of covariance (i.e., the number of two groups with three repeated measurements, adjusted for individual differences in baseline assessments). Allowing for an attrition rate of 40% that was observed in the previous study, a total of 50 parent-child dyads (25 in each group) will be recruited.

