2.7 Outcome Measures

2.7.1 Assessment timing

This pilot RCT will use four assessment points similar to the design of Graham et al.'s study. The four time points are: 5–6 weeks before intervention (time 0 for baseline assessment), 1–2 weeks before intervention (time 1 for pre-intervention assessment), 1–2 weeks after intervention (time 2 for post-intervention assessment), and 8–9 weeks after the intervention (time 3 for follow-up assessment).

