Young Children's Participation and Environment Measure (YC-PEM). The YC-PEM will be used to capture children's overall community participation patterns. This measure is selected because it is a parent report questionnaire that can be used for young children with various disabilities. The YC-PEM also has a community section that includes 11 participation items across four broad categories of neighbourhood and community outings, classes and groups, community-sponsored activities, and recreational activities and trips. In each item, parents are asked to rate: (a) how often their child has participated in the past four months using an 8-point Likert scale (0 = *never* and 7 = *once or more each day*); (b) how involved the child is during participation using a 5-point Likert scale (1 = *not very involved* and 5 = *very involved*); and (c) parental desire for change in the child's participation (yes/no and, if yes, six nominal options for the type of desired change can be selected). Total scores are generated by averaging all items in the participation frequency and involvement dimensions. High scores indicate greater children's participation frequency and involvement. The YC-PEM participation scale has acceptable internal consistency ($\alpha = 0.64$ – 0.78) and test-retest reliability (intraclass correlation coefficients [ICC] = 0.82–0.89). Moreover, it demonstrates known-group validity between children with and without disabilities and convergent validity by correlating with functional performance of children with disabilities.

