To evaluate the initial efficacy of OPC on the primary and secondary outcomes, we will use the repeated-measures analysis of covariance (ANCOVA) by controlling for baseline variability at time 0 as well as the variations in treatment dosage and delivery format (e.g., in person or tele-format). That is, the repeated-measures ANCOVAs will be used to compare the change in the scores of outcome measures across the three time points (at times 1, 2, and 3) by controlling for baseline differences and treatment variations. For participation goals identified by parents in the COPM, only community-related participation goals will be targeted for analysis. Principles of intent-to-treat analysis will be applied and, if participants withdraw after the coaching/consultation sessions, their data for subsequent time points will be imputed by carrying the last assessment forward. Post-hoc analyses using the Schffé method will be performed when the main comparison results are significant. Statistical significance will be set at $p < 0.05$. Estimates of effect sizes with 95% confidence intervals will be calculated for each outcome measure.

TABLE 1: A priori success criteria to assess the feasibility of the trial

	Definition	Success criteria
Recruitment	Percentage of eligible families agreeing to participate in the study	$\geq 20\%$ recruitment response rate achieved
Retention	Percentage of participants who complete the trial	$\geq 60\%$ retention rate achieved (i.e., completion of all assessments)
Adherence	Percentage of coaching sessions attended by parents in the intervention group	$\geq 75\%$ adherence rate achieved, based on our previous research of similar duration (42)
Blinding success	Percentage of parents who guess treatment allocation correctly after the study	50% based on the guess of treatment by chance (50/50)
Fidelity	Degree to which the OPC is implemented by coaches as intended	$\geq 80\%$ fidelity on the OPC Fidelity Measure Version 3.0 in four selected session per coach

Note: The OPC Fidelity Measure Version 3.0 consists of 18 items across five domains: relationship, goal, reflection, analysis and action, client response, and distinguishing. Each item is rated on a 3-point Likert scale (1 = *low* and 3 = *high*). The percentage score will be calculated by dividing the total score by the possible maximum score. Higher percentage scores indicate higher fidelity, and the cut-off of sufficient fidelity of OPC per session is set at 80%.

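### The 90% power behind 30 completers belongs to a different test from the one in section 2.8, because one of the three outcome measurements (Time 1) is taken before the intervention

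*Combined protocol and SAP*

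**What the plan says.** - **Section 2.3 (Sample Size)** uses a published formula with "power of 0.90, 1-to-1 random allocation, and variance ratio of 0.44, using a conservative assumption for the compound symmetry correlation structure" and Cohen's d of 0.80. It arrives at a minimum of 30 participants for a two-group ANCOVA, described as "the number of two groups with three repeated measurements, adjusted for individual differences in baseline assessments". Allowing for 40% attrition, 50 dyads are recruited. No between-occasion correlation is stated.
- **Section 2.7.1 (Assessment timing)** sets four assessments. Time 0 and Time 1 both precede treatment; Time 1 is 1–2 "weeks before intervention (time 1 for pre-intervention assessment". Times 2 and 3 follow treatment.
- **Section 2.8 (Data Analysis)** takes Time 0 as the covariate and uses the model to "compare the change in the scores of outcome measures across the three time points (at times 1, 2, and 3". It does not name the tested term. It says only that post-hoc comparisons "will be performed when the main comparison results are significant". For participants who withdraw after the sessions, "their data for subsequent time points will be imputed by carrying the last assessment forward".

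**The concern.** Section 2.3 counts three outcome measurements, and section 2.8 identifies them as Times 1, 2 and 3. Time 1 precedes treatment, so the expected group difference there is zero. A calculation that assumes 0.80 SD averaged over three outcomes does not describe an analysis in which one of the three cannot differ. Nor does it describe a test of change over time, whose variance depends on the correlation in another way.

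The 90% figure is the only reason given for 30 completers and 50 recruited, and efficacy is tested at p < 0.05. A non-significant result from a trial described as having 90% power could be read as evidence against a 0.80 SD effect when the power to detect one was much lower.

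**Working it through.** **Inputs from section 2.3:** alpha 0.05 (taken as two-sided, because that reproduces 30; one-sided gives 24), power 0.90, 1:1 allocation, d = 0.80, variance ratio 0.44, attrition 40%.

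**Assumptions not in the plan:** compound symmetry with correlation r at every pair of times, no effect at Time 1, 0.80 SD at each of Times 2 and 3, 15 completers per arm. The dosage and delivery-format covariates are ignored.

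**1. Reproduce the plan.** Unadjusted total N = 4 × (1.960 + 1.2816)² / 0.64 = 65.67. Times 0.44 this is 28.90; times 4/9 it is 29.19. Either way the result is 15 per arm, N = 30. Then 30 / (1 − 0.40) = 50. Both figures agree with the plan.

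**2. Where 0.44 comes from.** For the mean of k measurements adjusted for one baseline, the variance ratio is (1 + (k − 1)r)/k − r².
- k = 3: the maximum is 4/9 = 0.444, at r = 1/3. This fits three measurements, the word conservative and 0.44 together. It powers 0.80 SD averaged over all three measurements: 0.908 by normal approximation, 0.886 by t on 27 df.
- k = 2, r = 0.6: 1.6/2 − 0.36 = 0.44. This would power Times 2–3 given Time 0. It fits the wording poorly, and section 2.8 does not test it.

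**3. Power of the terms that section 2.8 could mean.** For the t tests the noncentrality is d × √(n/(2V)), with n per arm.
- Group effect averaged over Times 1–3: d = 0.80 × 2/3 = 0.533, V = (1 + 2r)/3 − r², 27 df. At r = 1/3 the noncentrality is 2.19.
- Mean of Times 2–3 minus Time 1: d = 0.80, V = 1.5(1 − r), 28 df. At r = 1/3 the noncentrality is again 2.19.
- Group-by-time test: lambda = (n/2) × 0.4267/(1 − r), on 2 and 56 df, where 0.4267 = 0.64 × 2/3. At r = 1/3 lambda is 4.80.

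**4. Alternatives that use Times 2–3 only** (d = 0.80).
- Given Time 0: V = (1 + r)/2 − r², with maximum 0.5625 at r = 0.25.
- Given Times 0 and 1: V = (1 + r)/2 − 2r²/(1 + r), with maximum 0.536 at r = 0.155.

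| Power, 15 per arm | r = 0.2 | 1/3 | 0.5 | 0.6 | 0.7 | 0.82 |
|---|---|---|---|---|---|---|
| Averaged over Times 1–3 | 0.58 | 0.56 | 0.59 | 0.64 | 0.72 | 0.87 |
| Times 2–3 minus Time 1 | 0.49 | 0.56 | 0.69 | 0.78 | 0.88 | 0.98 |
| Group-by-time, 2 df | 0.40 | 0.47 | 0.59 | 0.69 | 0.82 | 0.97 |
| Times 2–3 given Time 0 | 0.81 | 0.81 | 0.85 | 0.89 | 0.94 | 0.99 |
| Times 2–3 given Times 0 and 1 | 0.82 | 0.85 | 0.90 | 0.95 | 0.98 | >0.99 |

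The first three rows reach 90% at r of about 0.84, 0.72 and 0.76; the last two at about 0.62 and 0.49. The normal approximation adds up to 3 points to the t rows. Simulation (5,000 trials per r, at r = 0.2, 1/3 and 0.6) agreed to within about 2 points.

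**5. All 50 analysed** (order: averaged, contrast, group-by-time).
- Full data: 0.79, 0.79, 0.70 at r = 1/3; 0.86, 0.95, 0.91 at r = 0.6.
- Simulated, 40% withdrawing with the last value carried forward, half of them before Time 2: 0.49, 0.65, 0.61 at r = 1/3; 0.57, 0.85, 0.82 at r = 0.6.

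**6. Scale of d.** To average 0.80 SD over Times 1–3, the difference at Times 2 and 3 would have to be 0.80 × 3/2 = 1.20 SD. If 0.80 was meant in SDs of the change score, power for the contrast is 0.56 whatever r is.

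**The case against.** The arithmetic in section 2.3 is right; the objection is to what it is applied to. The strongest points on the other side are these.

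- **The correlation is inferred.** This stands. At k = 3 an exact 0.44 also fits r = 0.40 (power 0.51–0.61) or r = 0.27. Two post-treatment measurements given two baselines yield 0.44 at r = 0.46, and one post-treatment measurement yields 0.4375 at r = 0.75. At r = 0.75 the contrast would pass 90%, but a single measurement does not fit the three that section 2.3 describes.
- **The true correlation may be high.** For the YC-PEM the plan cites "test-retest reliability (intraclass correlation coefficients [ICC] = 0.82–0.89". At 0.82 the three terms have 0.87, 0.98 and 0.97. However, test-retest reliability may overstate the correlation across an intervention period, and none is given for the COPM. At r = 0.82 the k = 3 ratio would also be 0.21, not 0.44. One calculation cannot use a cautious r for N and a favourable r for power.
- **Section 2.8 analyses withdrawals too.** True, and power can then exceed 90%: with full data on all 50 and r = 0.6, two of the three terms do. But section 2.3 rests its 90% on 30, and carrying values forward does not restore the lost information.
- **The single contrast is not named in section 2.8.** Also true. It is included because the text speaks of change. Without it, the upper figure at r = 0.6 is 0.69 rather than 0.78.
- **This is a pilot.** Feasibility and acceptability are unaffected, and the planned effect sizes with 95% confidence intervals reduce the risk of misreading. Efficacy is still a stated aim with a significance test.

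**Conclusion.** The concern holds. Sections 2.3, 2.7.1 and 2.8 cannot all be right about what the 90% describes: one of the three sized outcomes precedes treatment. At the two correlations that best explain 0.44, every plausible tested term falls short with 30 completers: 47–56% at r = 1/3 and 64–78% at r = 0.6.

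The mismatch itself is certain. The size of the shortfall is conditional on the unstated correlation, the unstated tested term and the assumption of compound symmetry, and it largely disappears if r is above about 0.8. The dilution of the effect by one third applies only to the averaged group effect, which fits the wording of section 2.8 less well than a test of change.

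**What to change.** **Preferred.** In section 2.8, define the efficacy effect as the group difference averaged over Times 2 and 3, with Times 0 and 1 as baseline covariates (Time 0 alone is second choice). In section 2.3, state the correlation and replace 0.44 with the matching conservative ratio: 0.536 with two baselines, 0.5625 with one. Restate power for 30 completers as about 82% or 80% respectively by the t test (85% or 83% by normal approximation).

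**Minimum, if Time 1 stays an outcome level.** Name the tested term, state and justify the correlation, and restate power for that term.

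**Cost.** No extra recruitment or data. Under the preferred change Time 1 moves from outcome to covariate, and the stated power becomes less favourable. Keeping 90% at the conservative ratios would need 65.67 × 0.536 ≈ 35.2, so 36 completers, or 65.67 × 0.5625 = 36.9, so 38 (normal approximation).

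With Time 0 as the only covariate, the change does not always help once values are carried forward. At r = 0.6, with 40% withdrawing and half of them before Time 2, it has 0.83 against 0.85 for the contrast. The two-baseline version has 0.93 there and was highest in every scenario checked.

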2.4 Recruitment Method

Participants will be recruited from early intervention services within three non-governmental organizations in Hong Kong. Occupational therapists who work in each service will assist in the initial screening of potentially eligible families of children receiving services. They will then provide the parents of interest with the study information sheet and consent form. Once the signed consent forms are returned, a research assistant who oversees the trial will contact parents by phone to further screen for study participation eligibility. Posters and social media will be used to recruit families of children who are awaiting early intervention services. Parents of interest will be asked to contact the same research assistant for screening and, if eligible, to complete the consent forms.

2.5 Randomization and Blinding

Block randomization stratified by engagement in early intervention services (awaiting vs. receiving) based on the 1-to-1 allocation ratio will be used to assign participants to the intervention or control group. The randomization sequence will be computer-generated, and allocation will be completed by another research assistant not associated with the study.

Participants and independent outcome assessors will be blinded.

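### The efficacy model omits the awaiting/receiving stratum used in randomization, and sections 2.7.2.3.3 and 2.8 give different covariate lists

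*Combined protocol and SAP*

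**What the plan says.** Three sections of the combined protocol and SAP bear on this.

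- **2.5 Randomization and Blinding** specifies "Block randomization stratified by engagement in early intervention services (awaiting vs. receiving) based on the 1-to-1 allocation ratio". The factor has two levels. Block size and the expected split between strata are not given.
- **2.8 Data Analysis** evaluates primary and secondary outcomes by repeated-measures ANCOVA over times 1, 2 and 3, "controlling for baseline variability at time 0 as well as the variations in treatment dosage and delivery format". Neither the stratum nor any other service variable is named.
- **2.7.2.3.3 Other Exploratory Measures** observes that access to and intensity of early intervention may influence function and participation. It says that total service hours over the past month, grouped into categories, will be adjusted for in the efficacy analysis. No cut-points are given.

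The sample size in 2.3 rests on "type I error of 0.05, power of 0.90", on "1-to-1 random allocation, and variance ratio of 0.44", and on an effect size of 0.80. It has no term for the stratum.

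**The concern.** Stratified blocks balance the arms within each stratum, so differences between strata contribute almost nothing to the treatment contrast. If the analysis ignores the stratum, those differences stay in the residual variance. The standard error then exceeds the real sampling variability of the contrast: intervals are too wide, and the test rejects less often than 5% under the null. The error is conservative and does not bias the treatment estimate. What is at stake is precision, in a small pilot whose effect sizes and 95% intervals (promised in 2.8 for every outcome) are likely to inform a later trial.

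There is also a specification problem. An analyst following 2.8 literally would include no service variable. One who also read 2.7.2.3.3 would add service hours, with categories still to be chosen. Neither would include the factor used in the randomization.

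**Working it through.** **Reproducing the plan's own figure.** Inputs, all from 2.3: "type I error of 0.05, power of 0.90"; "A large effect size (Cohen's d) of 0.80 was determined"; "variance ratio of 0.44, using a conservative assumption for the compound symmetry correlation structure". Sidedness is not stated.

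n per arm = 0.44 × 2(z₀.₉₇₅ + z₀.₉₀)² / 0.80² = 0.44 × 32.84 = 14.45, rounded up to 15, so 30 in total. This agrees with "a minimum sample size of 30 participants will be required in this pilot RCT". A one-sided test would give 0.44 × 26.76 = 11.78, so 12 per arm and 24 in total; the plan's figure is therefore two-sided. Allowing for 40% attrition, 30 / (1 − 0.40) = 50. The stated numbers reproduce.

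**Effect of omitting the stratum, with no service covariate in the model.** Let R² be the share of baseline-adjusted residual variance that the stratum explains. The documents give no value; 0 to 0.20 is an assumed range. With n per arm:

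- SE reported without the stratum: s₀ = √0.44 × √(2/n)
- actual SE of the contrast: s₁ = s₀ × √(1 − R²)
- interval width ratio: s₀/s₁ = 1/√(1 − R²)
- type I error: 2[1 − Φ(1.96 × s₀/s₁)]
- power, stratum omitted: Φ((0.80 − 1.96 s₀)/s₁)
- power, stratum included: Φ(0.80/s₁ − 1.96)

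For n = 15, s₀ = 0.6633 × 0.3651 = 0.2422. At R² = 0.20, s₁ = 0.2166 and the width ratio is 1/√0.80 = 1.118.

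| R² (assumed) | Width ratio | Type I error, omitted | Power N=30, omitted / included | Power N=50, omitted / included |
|---|---|---|---|---|
| 0 | 1.000 | 5.0% | 91.04 / 91.04% | 98.94 / 98.94% |
| 0.05 | 1.026 | 4.4% | 91.59 / 92.35% | 99.10 / 99.21% |
| 0.10 | 1.054 | 3.9% | 92.15 / 93.59% | 99.24 / 99.44% |
| 0.20 | 1.118 | 2.8% | 93.34 / 95.84% | 99.50 / 99.75% |

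The power loss is 0, 0.76, 1.44 and 2.50 points at N=30, and at most 0.25 point at N=50.

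**Whether service hours can stand in for the stratum.** This was simulated with 3,000 trials per setting. The assumptions were blocks of 4, a 50/50 stratum split, and one outcome with a baseline covariate that leaves residual variance 0.44. Dosage and delivery format were not modelled. Hours had three categories: 20% of awaiting children report some hours, and receiving children split evenly between low and high. Results at N=30, in the order no service covariate / stratum / hours:

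| R² | Mean interval width | Power | Type I error |
|---|---|---|---|
| 0 | 1.005 / 1.008 / 1.036 | 86.4 / 86.4 / 85.1% | 4.9 / 5.0 / 4.7% |
| 0.05 | 1.004 / 0.981 / 1.014 | 86.8 / 88.3 / 86.1% | 3.9 / 4.6 / 4.8% |
| 0.10 | 1.008 / 0.955 / 0.997 | 87.5 / 90.2 / 88.0% | 4.0 / 4.6 / 5.0% |
| 0.20 | 1.011 / 0.902 / 0.960 | 90.1 / 94.2 / 90.8% | 3.3 / 5.3 / 5.5% |

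Monte Carlo standard error is about √(0.05 × 0.95/3000) = 0.4 point for type I error and about 0.5 point for power near 90%. The largest loss from omitting the stratum is 94.2 − 90.1 = 4.1 points. At N=50 and R² = 0.20, power is 99.2 / 99.5 / 99.2% and mean width is 0.765 / 0.680 / 0.715.

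In this scenario hours bring type I error back to about 5%. At R² = 0.20 they recover about half of the lost width at N=30: (1.011 − 0.960)/(1.011 − 0.902) = 0.47. At R² = 0.05 they recover none.

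**The case against.** The strongest reply is that the plan does adjust for service access. Section 2.7.2.3.3 commits to service hours in the efficacy analysis, and hours measure much the same thing as the stratum while adding intensity. This largely stands. A reader of 2.8 alone might infer that service access is ignored; the document as a whole does not support that. With hours in the model, the simulation shows no clear shortfall in type I error.

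The reply does not close the point. Hours are not the randomization factor: a receiving child could report none in the past month, and an awaiting child could report some. The strata also differ in recruitment route (2.4: therapist screening within services, as against posters and social media), which hours need not capture. And 2.8, which specifies the model, does not mention hours.

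A reader might also infer that intervals will certainly be too wide and power lost. The documents do not support that either. They say only that services may matter, with no size given, and 2.6.3 expects usual occupational therapy to affect community participation minimally. If the stratum adds nothing after baseline adjustment, nothing is lost.

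Finally, someone working from a single post-treatment score without baseline adjustment would find power of about 79% at 25 per arm, and a loss of several points. That is not the planned analysis: 2.3 uses a baseline-adjusted repeated-measures variance ratio of 0.44, which puts power near 99% at that size.

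**Conclusion.** The point holds as a modest one. The randomization stratum appears in no statement of the efficacy model, and the covariate lists in 2.7.2.3.3 and 2.8 disagree. Any statistical cost is conservative and conditional on the stratum being prognostic after adjustment for the time 0 score.

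Against a model with no service covariate, over assumed R² of 0 to 0.20, intervals are 0 to 12% too wide and type I error lies between 5.0% and 2.8%. Power falls by under 1 point at N=50 and by about 0 to 4 points at N=30. N=30 is what remains after the planned 40% attrition; because 2.8 carries the last assessment forward for some withdrawals, the analysed number may be larger and the loss smaller. Adjusting for service hours would reduce the cost, by an amount that depends on how closely hours track the stratum. The width and power figures rest on the assumed R² values, and the comparison with hours also on the assumed block size, stratum split and overlap. None of this inflates false positives or undermines the sample size of 30, raised to 50.

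**What to change.** In 2.8, give a single covariate list for all primary and secondary efficacy models. Include the randomization stratum (awaiting or receiving, as recorded at allocation) as a fixed effect. Reconcile the list with 2.7.2.3.3 by stating whether categorized service hours are also included and, if so, fix the cut-points before the data are examined. If both are kept, say so explicitly, because they overlap.

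The cost is one sentence and 1 df for the stratum, using a variable that allocation already requires. If the stratum proves unrelated to outcome, t-based power at 15 per arm falls only from 88.94% to 88.85%. Service hours are not quite as cheap: with three categories and no prognostic value, they widened the simulated interval at N=30 by about 3% (1.036/1.005 = 1.031), so adding them to the stratum should be a deliberate choice. The planned sample size does not change.
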